5.2.3 Duration of Participation

Subjects will remain on study for up to 2 years. Subjects who are benefiting from therapy (SD/PR/CR) as judged by the treating investigator may continue on active treatment with pembrolizumab for up to 2 years.

5.3 Treatment Allocation

In the Phase Ib portion of the study, accrual will start with the lowest dose of IL-2 (6,000 IU/kg IV Q 8 hours) with a cohort size of 3 subjects and proceed to higher doses. Please see Section 8 for dose escalation procedure.

In the Phase II expansion cohort, all subjects will be treated with the MTD of IL-2 according to the same schedule with pembrolizumab.

There will be no randomization or within-subject dose escalation.

5.4 Dose Modification/Withholding

5.4.1 Dose Modifications of Pembrolizumab

No dose reductions of pembrolizumab are allowed.

Adverse events (both non-serious and serious) associated with pembrolizumab exposure may represent an immunologic etiology. These adverse events may occur shortly after the first dose or several months after the last dose of treatment.

Pembrolizumab must be withheld (not delayed) for drug-related toxicities and severe or life-threatening AEs as per Table 3 below. See Section 5.4 and Events of Clinical Interest Guidance Document for supportive care guidelines and management recommendations, including use of corticosteroids.

If criteria for resuming treatment are met, pembrolizumab treatment should resume at the next scheduled treatment timepoint (3 weeks later), or be permanently discontinued as per Table 3 below.

Although no dose delays for toxicity are allowed, an administrative delay within the allotted window of ± 7 days is allowed as per the Trial Flow Chart (Section 6.0). The next dose should be given when it is due according to the Trial Flow Chart with the goal of maintaining a consistent treatment schedule across all patients.

Dosing interruptions are permitted in the case of medical / surgical events or logistical reasons not related to study therapy (e.g., elective surgery, unrelated medical events, patient vacation, and/or holidays). Subjects should be placed back on study therapy within 3 weeks of the scheduled interruption, unless otherwise discussed with the study PI or co-PI. The reason for interruption should be documented in the patient's study record.

Table 3. Dose Modification and Toxicity Management Guidelines for Immune-related AEs Associated with Pembrolizumab

General instructions:				

 Corticosteroid taper should be initiated upon AE improving to Grade 1 or less and continue to taper over at least 4 weeks. For situations where pembrolizumab has been withheld, pembrolizumab can be resumed after AE has been reduced to Grade 1 or 0 and corticosteroid has been tapered. Pembrolizumab should be permanently discontinued if AE does not resolve within 12 weeks of last dose or corticosteroids cannot be reduced to ≤ 10 mg prednisone or equivalent per day within 12 weeks. For severe and life-threatening irAEs, IV corticosteroid should be initiated first followed by oral steroid. Other immunosuppressive treatment should be initiated if irAEs cannot be controlled by corticosteroids. 				
Immune-related AEs	Toxicity grade or conditions (CTCAEv4.0)	Action taken to pembrolizumab	irAE management with corticosteroid and/or other therapies	Monitor and follow-up
Pneumonitis	Grade 2	Withhold	
 Administer corticosteroids (initial dose of 1-2 mg/kg prednisone or equivalent) followed by taper 	
 Monitor participants for signs and symptoms of pneumonitis Evaluate participants with suspected pneumonitis with radiographic imaging and initiate corticosteroid treatment Add prophylactic antibiotics for opportunistic infections
	Grade 3 or 4, or recurrent Grade 2	Permanently discontinue		
Diarrhea / Colitis	Grade 2 or 3	Withhold	
 Administer corticosteroids (initial dose of 1-2 mg/kg prednisone or equivalent) followed by taper 	
 Monitor participants for signs and symptoms of enterocolitis (ie, diarrhea, abdominal pain, blood or mucus in stool with or without fever) and of bowel perforation (ie, peritoneal signs and ileus). Participants with \geq Grade 2 diarrhea suspecting colitis should consider GI consultation and performing endoscopy to rule out colitis. Participants with diarrhea/colitis should be advised to drink liberal quantities of clear fluids. If sufficient oral fluid intake is not feasible, fluid and electrolytes should be substituted via IV infusion.
	Grade 4	Permanently discontinue		

AST / ALT elevation or increased bilirubin	Grade 2	Withhold	
 Administer corticosteroids (initial dose of 0.5- 1 mg/kg prednisone or equivalent) followed by taper 	
 Monitor with liver function tests (consider weekly or more frequently until liver enzyme value returned to baseline or is stable)
	Grade 3 or 4	Permanently discontinue	
 Administer corticosteroids (initial dose of 1-2 mg/kg prednisone or equivalent) followed by taper 	
Type 1 diabetes mellitus (T1DM) or Hyperglycemia	Newly onset T1DM or Grade 3 or 4 hyperglycemia associated with evidence of β -cell failure	Withhold	
 Initiate insulin replacement therapy for participants with T1DM Administer anti-hyperglycemic in participants with hyperglycemia 	
 Monitor participants for hyperglycemia or other signs and symptoms of diabetes.
	Grade 2	Withhold	
 Administer corticosteroids and initiate hormonal replacements as clinically indicated. 	
 Monitor for signs and symptoms of hypophysitis (including hypopituitarism and adrenal insufficiency)
Hypothyroidism	Grade 2	Continue	
 Treat with non-selective beta-blockers (eg, propranolol) or thionamides as appropriate 	
 Monitor for signs and symptoms of thyroid disorders.
	Grade 3 or 4	Withhold or permanently discontinue ¹		
Hypothyroidism	Grade 2-4	Continue	
 Initiate thyroid replacement hormones (eg, levothyroxine or liothyronine) per standard of care Administer corticosteroids (prednisone 1-2 mg/kg or equivalent) followed by taper. 	
 Monitor for signs and symptoms of thyroid disorders. Monitor changes of renal function
	Grade 2	Withhold		
Nephritis and Renal dysfunction	Grade 3 or 4	Permanently discontinue		
	Grade 1 or 2	Withhold	
 Based on severity of AE administer corticosteroids 	
 Ensure adequate evaluation to confirm etiology and/or exclude other causes
Myocarditis	Grade 3 or 4	Permanently discontinue		

All other immune-related AEs	Intolerable/persistent Grade 2	Withhold	
 Based on type and severity of AE administer corticosteroids 	
 Ensure adequate evaluation to confirm etiology and/or exclude other causes
	Grade 3	Withhold or discontinue based on the type of event. Events that require discontinuation include and not limited to: Guillain-Barre Syndrome, encephalitis		
	Grade 4 or recurrent Grade 3	Permanently discontinue		

1. Withhold or permanently discontinue pembrolizumab is at the discretion of the investigator or treating physician.

NOTE:
For participants with Grade 3 or 4 immune-related endocrinopathy where withhold of pembrolizumab is required, pembrolizumab may be resumed when AE resolves to \leq Grade 2 and is controlled with hormonal replacement therapy or achieved metabolic control (in case of T1DM).

Please refer to Section 5.6 Rescue Medications and Supportive Care for additional information on toxicity management.

5.4.2 Dose Modifications of IL-2

No dose reductions or dose escalations of IL-2 are allowed (other than the use of ideal body weight for dose calculations, which is permitted. See Section 5.2.2).

Cycles of IL-2 may not be delayed beyond the window allotted in the Study Flow Chart in Section 6.0 (± 7 days).

Delays and omissions of the individual doses of IL-2 within a cycle are allowed. Dose delays will be administered according to investigator's judgment. Table 4 is provided as a guide for treating investigators (reproduced from the Proleukin package insert with permission).

Table 4. IL-2 Dose Holding and Restarting Guidelines for Drug-Related Adverse Events

Body System	Hold dose for	Subsequent doses may be given if
Cardiovascular	
Atrial fibrillation, supraventricular tachycardia or bradycardia that requires treatment or is recurrent or persistent
 
Systolic bp <90 mm Hg with increasing requirements for pressors
 
Any ECG change consistent with MI, ischemia or myocarditis with or without chest pain; suspicion of cardiac ischemia
	
Patient is asymptomatic with full recovery to normal sinus rhythm
 
Systolic bp \geq90 mm Hg and stable or improving requirements for pressors
 
Patient is asymptomatic, MI and myocarditis have been ruled out, clinical suspicion of angina is low; there is no evidence of ventricular hypokinesia

Respiratory	O2 saturation <90%	O2 saturation >90%
Nervous	Mental status changes, including moderate confusion or agitation	Mental status changes completely resolved
Body as a Whole	Sepsis syndrome, patient is clinically unstable	Sepsis syndrome has resolved, patient is clinically stable, infection is under treatment
Urogenital	
Serum creatinine >4.5 mg/dL or a serum creatinine of \geq4 mg/dL in the presence of severe volume overload, acidosis, or hyperkalemia
 
Persistent oliguria, urine output of <10 mL/hour for 16 to 24 hours with rising serum creatinine
	
Serum creatinine <4 mg/dL and fluid and electrolyte status is stable
 
Urine output >10 mL/hour with a decrease of serum creatinine >1.5 mg/dL or normalization of serum creatinine

Digestive	
Signs of hepatic failure including encephalopathy, increasing ascites, liver pain, hypoglycemia
 
Stool guaiac repeatedly >3-4+
	
All signs of hepatic failure have resolved
 
Stool guaiac negative

Skin	Bullous dermatitis or marked worsening of pre-existing skin condition, avoid topical steroid therapy	Resolution of all signs of bullous dermatitis

IL-2 will be permanently discontinued for any grade ≥ 4 hematological or ≥ 3 non-hematological adverse events that do not resolve to \leq grade 2 within 7 days of completing IL-2 treatment if the side effect is definitely related to IL-2. This will be considered an IL-2-related SAE (see Section 7.2.1.2), and the patient will not receive further IL-2. The patient may continue on study with pembrolizumab monotherapy at the discretion of the treating investigator.

5.4.1 Inpatient visits (both drugs scheduled to be given):

In the event that a patient is experiencing a significant pembrolizumab-related adverse event at the time that inpatient admission for IL-2 is scheduled (with ± 7 day window), the scheduled admission/therapy will be omitted (not delayed) until the pembrolizumab-related adverse event resolves to Grade 1 or less. Both drugs may be given at the next regularly scheduled timepoint.

If the following pembrolizumab-related adverse events are present, both drugs should be withheld, including:

- Any \geq Grade 2 non-skin related adverse event (including ECIs/irAEs), except for isolated laboratory abnormalities
- Any \geq Grade 3 laboratory abnormality
- Any adverse event, laboratory abnormality or intercurrent illness that, in the judgment of the investigator, presents a substantial clinical risk to the subject with continued dosing.

If these adverse events resolve to Grade 1 or less, treatment can be resumed at the next regularly scheduled timepoint. If there are questions about a specific patient, the investigator may contact the study PI for further discussion.

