5.2.1.2 Dosing

All subjects will be treated with pembrolizumab given at a flat dose of 200 mg IV every 3 weeks per Trial Flow Chart. The flat dose will be used whether given in combination with IL-2 or given as monotherapy.

Pembrolizumab 200 mg will be administered as a 30 minute IV infusion every 3 weeks. Sites should make every effort to target infusion timing to be as close to 30 minutes as possible. However, given the variability of infusion pumps from site to site, a window of -5 minutes and +10 minutes is permitted (i.e., infusion time is 30 minutes: -5 min/+10 min).

The Pharmacy Manual contains specific instructions for the preparation of the pembrolizumab infusion fluid and administration of infusion solution.

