Typically, 2 cycles of IL-2 make up a course of IL-2. The duration of a cycle is the duration of hospitalization (approximately 3-7 days). Admission for IL-2 will occur at Weeks 4, 7, 16, 19, 28, and 31 as per the Study Flow Chart in Section 6.0. IL-2 may not be given earlier or later than the allotted window (± 7 days). A minimum rest period of 9 days is required in between admissions to the hospital. If an admission for IL-2 is moved up or delayed, the pembrolizumab will be moved up or delayed as well to be given on the same day as the IL-2.

On days when pembrolizumab and IL-2 are scheduled to be administered together, pembrolizumab should be administered first, followed by IL-2 administration, which should commence 1-8 hours after the completion of pembrolizumab infusion.

The following should be done daily during IL-2 administration: neurologic assessment, complete blood count, blood chemistries, chest x-ray, vital signs, pulse oximetry, weight, and fluid intake and output.

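### At visits where both drugs are due, the inpatient rule permits pembrolizumab to be resumed after events for which Table 3 requires permanent discontinuation, and no text reviewed says which rule governs

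*SAP*

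**What the plan says.** Two parts of SAP Section 5.4 tell a site what to do with pembrolizumab when a patient has a pembrolizumab-related adverse event.

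**Section 5.4.1, Dose Modifications of Pembrolizumab, with Table 3.** The text makes withholding according to Table 3 mandatory. After a hold, pembrolizumab either resumes at the next scheduled time, if the criteria are met, "or be permanently discontinued as per Table 3 below". No exception is made for inpatient visits. Table 3 covers immune-related events associated with pembrolizumab. Its liver row, "AST / ALT elevation or increased bilirubin", withholds at Grade 2 and permanently discontinues at Grade 3-4. Its kidney row, "Nephritis and Renal dysfunction", permanently discontinues at Grade 3-4.

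**Inpatient visits (both drugs scheduled).** This subsection follows 5.4.2 and is numbered 5.4.1 a second time. Both drugs are withheld for three groups of pembrolizumab-related event:
- events at or above "Grade 2 non-skin related adverse event (including ECIs/irAEs), except for isolated laboratory abnormalities";
- any laboratory finding at or above "Grade 3 laboratory abnormality";
- anything that the investigator judges to be a substantial risk.

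It then adds: "If these adverse events resolve to Grade 1 or less, treatment can be resumed at the next regularly scheduled timepoint". An earlier sentence in the subsection says that both drugs may be given at that point.

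**The concern.** The inpatient text names immune-related events explicitly, so it covers the events that Table 3 governs. Its resume sentence applies to every event in its list, whatever the original grade, and has no carve-out for events that Table 3 stops for good. A site that reads the inpatient text as the specific rule for combined-dosing visits could re-expose a patient to pembrolizumab after a severe hepatic, renal, pulmonary or cardiac immune event. A site that reads Table 3 as controlling would stop pembrolizumab permanently in an identical patient.

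Safety is a primary objective (Section 3.1.1) and there is no control group. If sites differ, exposure, discontinuation and observed toxicity would partly reflect which text each site followed. The more immediate issue is patient safety: one written rule permits re-exposure that another forbids.

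**Working it through.** The plan states no figure on this point, so the check is a comparison of the two texts, plus one count of visits.

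**Step 1: which visits are affected.** Section 5.2.2.1: "Admission for IL-2 will occur at Weeks 4, 7, 16, 19, 28, and 31 as per the Study Flow Chart in Section 6.0". Section 5.2.1.2: "All subjects will be treated with pembrolizumab given at a flat dose of 200 mg IV every 3 weeks per Trial Flow Chart". Section 2.1 has one pembrolizumab dose given alone before combined dosing, which implies dosing from Week 1. The flow chart itself was not in the text reviewed. An IL-2 week falls on a pembrolizumab week if (week − 1) is divisible by 3:

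4 − 1 = 3; 7 − 1 = 6; 16 − 1 = 15; 19 − 1 = 18; 28 − 1 = 27; 31 − 1 = 30.

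All six coincide. Three-weekly visits from Week 1 to Week 31 number (31 − 1)/3 + 1 = 11, so up to 6 of the first 11 are combined visits. Six is a maximum. Under Section 5.2.2.5, IL-2 stops for complete response, certain toxicities or patient refusal, and repeat courses are for stable disease or partial response.

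**Step 2: events where Table 3 ends pembrolizumab.** Each row below meets an inpatient withholding trigger, so the inpatient resume sentence reaches it.

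| Immune-related event | Table 3, pembrolizumab | Inpatient text, once Grade 1 or less |
|---|---|---|
| AST/ALT or bilirubin, Grade 3-4 | Permanent stop | Both drugs may resume |
| Nephritis/renal dysfunction, Grade 3-4 | Permanent stop | Both drugs may resume |
| Pneumonitis, Grade 3-4 or a recurrent Grade 2 | Permanent stop | Both drugs may resume |
| Colitis, Grade 4 | Permanent stop | Both drugs may resume |
| Myocarditis, Grade 3-4 | Permanent stop | Both drugs may resume |
| Other non-skin immune events, Grade 4 or a recurrent Grade 3 | Permanent stop | Both drugs may resume |

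The liver row is the clearest. Table 3 defines it by laboratory values, and the inpatient list takes in every laboratory abnormality of Grade 3 or higher.

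**Step 3: Grade 2 laboratory events.**
- *Liver.* Table 3 withholds pembrolizumab for Grade 2 AST/ALT or bilirubin elevation. The inpatient text takes isolated laboratory abnormalities out of its Grade 2 trigger and sets the laboratory threshold at Grade 3. It therefore imposes no mandatory hold, although the investigator may still withhold.
- *Kidney.* The same conflict may exist, but less certainly. In the extracted table the Grade 2 line is displaced from its label and has to be read from its position. The conflict also depends on whether an isolated creatinine rise counts as renal dysfunction.

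**Step 4: scope.** The inpatient list concerns pembrolizumab-related events; Table 3 concerns immune-related ones. Only events that are both can conflict.

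**Step 5: precedence.** Neither text refers to the other to settle the matter. Because both subsections carry the number 5.4.1, a citation by number does not settle it either.

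**The case against.** The best answer is that the texts can be obeyed together. Section 5.4.1 is mandatory and has no inpatient exception, while the inpatient text only says that treatment can resume. A site that applies Table 3 to pembrolizumab first, and the inpatient text second, breaches neither. The inpatient text also keeps a discretionary hold and lets the investigator put patient-specific questions to the study PI.

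Three points in this stand:
- A reader might infer that the same patient must be both re-treated and permanently stopped. The documents do not say so: one rule permits what the other bars.
- A reader might infer that the inpatient text directs dosing despite an isolated Grade 2 laboratory event, so that the same result means a hold at Week 10 and treatment at Week 16. It only omits a mandatory hold, and nothing says that it displaces Table 3.
- A reader might try to count affected patients. The documents give no rate for these events. Section 4.1.3.2 calls creatinine and bilirubin rises frequent, but in trials of IL-2. That suggests attribution will be difficult, not how often the conflict arises.

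The objection does not remove the conflict. Reading Table 3 first is a choice the site has to make: the mandatory wording favours Table 3, and the specific-over-general principle favours the inpatient text. Discretion and an optional call to the PI do not say which applies.

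A further limit is that Sections 6 to 10 and the companion guidance on events of clinical interest were not in the text reviewed. A precedence statement could lie there.

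**Conclusion.** The conflict is real and is in the current text. At up to six combined-dosing visits, the inpatient rule allows pembrolizumab to be resumed after events for which Section 5.4.1 and Table 3 require a permanent stop. The firmest case is Grade 3-4 AST/ALT or bilirubin elevation, and five further groups of event follow from the same sentence. The Grade 2 liver conflict is secondary: no mandatory hold in one place, a hold in the other. The Grade 2 renal conflict is only possible.

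The conclusion rests on reading the resume sentence as covering every event in the list before it, and on the absence of a precedence rule elsewhere. Its size is the number of visits and table rows affected, not a number of patients. It warrants correction because it concerns re-exposure after severe immune toxicity in a trial whose primary objectives include safety. No view is taken here on which clinical rule is right.

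**What to change.** 1. Reconcile the inpatient-visit subsection with Table 3 row by row. For every row with a permanent stop, make the resume sentence and the table agree. For every row triggered by a laboratory value, make the Grade 2 action agree, and say whether an isolated creatinine rise falls under the renal row.
2. State in both places which text governs pembrolizumab when both drugs are due.
3. Renumber the second 5.4.1 so that cross-references are unambiguous.

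The sponsor's clinicians decide which rule stands. The cost is a wording amendment to one subsection and a table note, plus a memo to sites. It needs no extra patients, visits or procedures.

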- All subjects who experience diarrhea/colitis should be advised to drink liberal quantities of clear fluids. If sufficient oral fluid intake is not feasible, fluid and electrolytes should be substituted via IV infusion. For Grade 2 or higher diarrhea, consider GI consultation and endoscopy to confirm or rule out colitis.
- For **Grade 2 diarrhea/colitis** that persists greater than 3 days, administer oral corticosteroids.
- For **Grade 3 or 4 diarrhea/colitis** that persists > 1 week, treat with intravenous steroids followed by high dose oral steroids.
- When symptoms improve to Grade 1 or less, steroid taper should be started and continued over no less than 4 weeks.

- **Type 1 diabetes mellitus (if new onset, including diabetic ketoacidosis [DKA]) or \geq Grade 3 Hyperglycemia, if associated with ketosis (ketonuria) or metabolic acidosis (DKA)**
 - For **T1DM or Grade 3-4 Hyperglycemia**
 - Insulin replacement therapy is recommended for Type I diabetes mellitus and for Grade 3-4 hyperglycemia associated with metabolic acidosis or ketonuria.
 - Evaluate patients with serum glucose and a metabolic panel, urine ketones, glycosylated hemoglobin, and C-peptide.

- **Hypophysitis:**
 - For **Grade 2** events, treat with corticosteroids. When symptoms improve to Grade 1 or less, steroid taper should be started and continued over no less than 4 weeks. Replacement of appropriate hormones may be required as the steroid dose is tapered.
 - For **Grade 3-4** events, treat with an initial dose of IV corticosteroids followed by oral corticosteroids. When symptoms improve to Grade 1 or less, steroid taper should be started and continued over no less than 4 weeks. Replacement of appropriate hormones may be required as the steroid dose is tapered.

- **Hyperthyroidism or Hypothyroidism:**

Thyroid disorders can occur at any time during treatment. Monitor patients for changes in thyroid function (at the start of treatment, periodically during treatment, and as indicated based on clinical evaluation) and for clinical signs and symptoms of thyroid disorders.

 - **Grade 2 hyperthyroidism events (and Grade 2-4 hypothyroidism):**
 - In hyperthyroidism, non-selective beta-blockers (e.g. propranolol) are suggested as initial therapy.
 - In hypothyroidism, thyroid hormone replacement therapy, with levothyroxine or liothyronine, is indicated per standard of care.
 - **Grade 3-4 hyperthyroidism**

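### At combined-dosing visits the restart rule omits Table 3's steroid-taper condition, so for immune events managed by withholding plus corticosteroids the two rules disagree at the next 3-week visit

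*SAP*

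**What the plan says.** All of this is in the SAP document, where two sections carry the number 5.4.1.

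- **Section 5.4.1, Inpatient visits (placed after 5.4.2).** If a significant pembrolizumab-related event is present when an admission is due, the admission is omitted and both drugs are withheld. The listed triggers include Grade 2 or higher "non-skin related adverse event (including ECIs/irAEs), except for isolated laboratory abnormalities". Restart needs only the grade: "If these adverse events resolve to Grade 1 or less, treatment can be resumed at the next regularly scheduled timepoint", and "Both drugs may be given at the next regularly scheduled timepoint". The section has no steroid condition and does not refer to Table 3.
- **Section 5.4.1, Dose Modifications of Pembrolizumab, Table 3 general instructions.** Here there are two conditions: "pembrolizumab can be resumed after AE has been reduced to Grade 1 or 0 and corticosteroid has been tapered". The taper has a fixed start and a minimum length: "Corticosteroid taper should be initiated upon AE improving to Grade 1 or less and continue to taper over at least 4 weeks".
- **Section 5.6.1** repeats that minimum for several organ systems: "When symptoms improve to Grade 1 or less, steroid taper should be started and continued over no less than 4 weeks".
- **Section 5.4.1, text before Table 3.** Provided the resumption criteria are met, "pembrolizumab treatment should resume at the next scheduled treatment timepoint (3 weeks later"). The text adds "Although no dose delays for toxicity are allowed", and leaves only an administrative window of 7 days either side.
- **Section 5.2.2.1** fixes IL-2 admissions at Weeks 4, 7, 16, 19, 28 and 31, with the same window.

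Table 3 governs pembrolizumab only. For IL-2, the inpatient section holds the only restart rule tied to a pembrolizumab-related event.

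**The concern.** The two restart rules cover overlapping events. Grade 2 pneumonitis and Grade 2 or 3 colitis, for example, trigger the inpatient rule, and Table 3 manages both by withholding pembrolizumab and giving corticosteroids. Once such an event is at Grade 1, the inpatient section permits both drugs at the next timepoint, while Table 3 does not permit pembrolizumab until the steroid has been tapered. Nothing in the available text says which rule prevails at an inpatient visit.

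Two things are at stake. First, a site that follows the visit-specific rule as written could give pembrolizumab again during a taper, which Table 3 does not allow. Second, a site that follows Table 3 for pembrolizumab is not told whether the IL-2 admission then goes ahead alone or is omitted. The same event can therefore lead to different exposure to the combination at different sites, and the safety and efficacy of that combination are the primary objectives.

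**Working it through.** The plan gives no figure to reproduce; the check is calendar arithmetic.

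**Inputs**
- Visit spacing: 21 days (Section 5.4.1, pembrolizumab).
- Window: up to +7 days. It is administrative, so counting it here is generous to the plan.
- Taper: starts on day *r*, when the event reaches Grade 1 or less, counted from the withheld visit (*r* = 0 to 20 within one interval). Minimum length 28 days (Table 3, Section 5.6.1).
- Gaps between IL-2 admissions (Section 5.2.2.1): 3, 9, 3, 9 and 3 weeks, that is 21, 63, 21, 63 and 21 days.

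**Formula.** A complete taper ends on day *r* + 28 at the earliest. The rules disagree at a visit on day *V* if *r* + 28 > *V*.

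**1. Next 3-week visit**
- *V* = 21: *r* + 28 > 21 for every *r*, so 21 of 21 days conflict.
- *V* = 21 + 7 = 28: conflict for *r* = 1 to 20, so 20 of 21 days (95%). The exception is *r* = 0 with a taper of exactly 28 days.

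**2. First visit that satisfies Table 3** (smallest *k* with 21*k* ≥ *r* + 28)
- *r* = 0 to 14: day 42 (15 of 21 days).
- *r* = 15 to 20: day 63 (6 of 21 days).

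**3. Example.** Both drugs are withheld at Week 4 and Grade 1 is reached 10 days later. The inpatient rule permits both drugs at Week 7 (day 21). Under Table 3 the taper ends on day 10 + 28 = 38 at the earliest, so pembrolizumab restarts at Week 10 (day 42). Whether IL-2 is given alone at Week 7 is not stated. If it is omitted, the next admission is Week 16.

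**4. If the next timepoint means the next IL-2 admission**

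| Withheld admission | Days to next admission | Conflict, nominal | Conflict, +7 days |
|---|---|---|---|
| Week 4, 16 or 28 | 21 | 21 of 21 | 20 of 21 |
| Week 7 or 19 | 63 | 27 of 63 (43%), only if *r* > 35 | 20 of 63 (32%), only if *r* > 42 |
| Week 31 | none left | – | – |

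After Weeks 7 and 19, an event that reaches Grade 1 within 20 days has a minimum taper ending by day 20 + 28 = 48, before day 63.

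**5. If *tapered* means a low dose.** Table 3's only numeric steroid level is 10 mg prednisone per day, and it belongs to the permanent-discontinuation rule. Assume that it also defines *tapered*, and assume a linear 28-day taper from dose *D*. Then 10 mg is reached on day 28 × (1 − 10/*D*). Table 3 starting doses run from 0.5 to 2 mg/kg; assuming body weights of 60 to 100 kg, *D* runs from 30 to 200 mg.
- *D* = 30: day 18.7. Conflict on 18 of 21 days nominally, 11 of 21 with the window.
- *D* = 200: day 26.6. Conflict on 21 of 21 days nominally, 19 of 21 with the window.

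All of these counts are calendar days, not frequencies of events.

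**The case against.** The strongest reply is that both rules can be obeyed together. The inpatient section only permits restart, whereas the pembrolizumab section requires withholding according to Table 3 and makes resumption depend on its criteria. Nothing confines Table 3 to outpatient visits. A site that applies the stricter rule breaches neither passage. That is fair for pembrolizumab, but the inpatient section does not say so, and as the visit-specific rule it can reasonably be read as controlling. It also leaves IL-2 open, because Table 3 does not govern IL-2.

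There are other safeguards. Section 5.2.2.1 requires concomitant medications to be reviewed before each IL-2 cycle and refers to institutional and practice guidelines. The inpatient section withholds both drugs for anything that the investigator judges a substantial risk, and offers contact with the study PI. These reduce the hazard but do not state a restart condition, and a site reading only the inpatient section may see no question to raise. The Section 6.0 flow chart and the companion Events of Clinical Interest guidance are not in the material supplied and might bear on the point.

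A reader might infer that nearly every steroid-treated event is caught. The documents do not support that. Table 3 permanently discontinues pembrolizumab for several such events (for example Grade 3 or 4 pneumonitis and Grade 4 colitis), so no taper question arises. Its closing note gives Grade 3 or 4 endocrinopathy a separate restart rule. Isolated Grade 2 laboratory abnormalities fall outside the listed Grade 2 trigger. Nor are all six combined visits affected alike for IL-2, as the table shows.

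A reader might also cite exclusion criterion 3, on steroids in the 7 days before first dose. That is an entry rule; Section 5.5.2 exempts on-study steroids given for immune events.

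**Conclusion.** The point holds for pembrolizumab-related immune events that Table 3 manages by withholding plus corticosteroids, leaving aside permanent discontinuations and the Grade 3 or 4 endocrinopathy exception. For those events, with a complete taper and the next timepoint taken as the next 3-week visit, the rules disagree on every possible resolution day, or on 20 of 21 with the full window. Under the assumed low-dose reading the conflict is smaller: 18 to 21 of 21 days nominally, 11 to 19 with the window.

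For IL-2 the consequence arises mainly when the withheld admission is Week 4, 16 or 28. After Weeks 7 and 19 a minimum taper usually ends in time, and after Week 31 no IL-2 remains.

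This is more than a missing cross-reference, because one passage permits what the other does not. It would go too far to infer that response or tolerability results will be distorted: the documents give no frequency for these events, so that effect cannot be sized.

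**What to change.** Reconcile the inpatient section with Table 3 by a short amendment that states:

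1. which restart condition governs pembrolizumab and which governs IL-2 at combined visits;
2. whether the next timepoint there means the next 3-week visit or the next IL-2 admission;
3. what *tapered* means: steroid stopped, or reduced to a named dose;
4. whether the IL-2 admission is given or omitted when pembrolizumab may not yet restart.

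The investigators should choose the clinical rule; this review takes no position on it. Giving the second Section 5.4.1 its own number would also help.

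For the analysis, use the concomitant-medication data already collected on the CRF (Section 5.5.1) to flag IL-2 cycles given under systemic corticosteroids.

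The cost is a short amendment and a site memo. Depending on the rule chosen, some IL-2 cycles will be omitted or some will be flagged as given under steroids.
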